13.3 Stratification Factors

Patients will be stratified based on HPV status. Any commonly used HPV test is acceptable (e.g. p16 IHC, HPV ISH, etc). If HPV status is not available, slides can be sent to the University of Chicago and HPV testing will be performed. No interim monitoring or efficacy analysis will be done based on this stratification. The goal is primarily to ascertain comparability between the two treatment arms. Please note that p16 IHC is generally only considered accurate if performed in oropharyngeal tumors and retesting in other anatomic sites may be necessary.

13.4 Analysis of Secondary Endpoints

Secondary endpoints will include change in tumor burden (sum of longest diameters of target lesions) from baseline to 8 weeks, PFS, and OS. Early change in tumor burden will be compared between groups using two-sample t-tests. Waterfall plots will be constructed for graphical comparison. In the event that early deaths within 8 weeks or dropouts occur, nonparametric Wilcoxon rank-sum tests will be performed in place of t-tests, with such patients assigned the worst ranking (*Karrison et al, JNCI, 2007*). Kaplan-Meier curves will be generated for PFS and OS and the treatment arms compared via logrank tests. We will also fit logistic and Cox (JRSS, 1972) proportional hazards regression models to examine the effects of laboratory correlates on response, PFS, and OS.

Finally, each of the primary and secondary endpoints will be compared between treatment arms among the subgroup of patients with high c-MET expression and/or high c-MET copy number in an exploratory fashion.

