Target lesions. All measurable lesions up to a maximum of 2 lesions per organ and 5 lesions in total, representative of all involved organs, should be identified as **target lesions** and recorded and measured at baseline. Target lesions should be selected on the basis of their size (lesions with the longest diameter), be representative of all involved organs, but in addition should be those that lend themselves to reproducible repeated measurements. It may be the case that, on occasion, the largest lesion does not lend itself to reproducible measurement in which circumstance the next largest lesion which can be measured reproducibly should be selected. A sum of the diameters (longest for non-nodal lesions, short axis for nodal lesions) for all target lesions will be calculated and reported as the baseline sum diameters. If lymph nodes are to be included in the sum, then only the short axis is added into the sum. The baseline sum diameters will be used as reference to further characterize any objective tumor regression in the measurable dimension of the disease.

Non-target lesions. All other lesions (or sites of disease) including any measurable lesions over and above the 5 target lesions should be identified as **non-target lesions** and should also be recorded at baseline. Measurements of these lesions are not required, but the presence, absence, or in rare cases unequivocal progression of each should be noted throughout follow-up.

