13.2 Sample Size/Accrual Rate

We expect to jointly enroll 3-6 patients per month for a total of 76 response evaluable patients (38 patients in each arm) over a period of 18-24 months. Patients will then be followed for at least 6 months.

Comparison of combination arm with single agent cetuximab: Response rates in the two arms will be compared using a continuity-corrected chisquare test. A sample size of n=38 patients per arm will provide 80% power to detect a difference of 12% vs. 35% between the cetuximab and combination treatment arms, using a one-sided test at the alpha=0.10 significance level.

Effect Size: We are assuming a comparably large effect size based on the following rationale:

- Preclinical data suggests high expression levels of MET and EGFR (higher than e.g. for NSCLC) as well as strong synergy for combined inhibition (see above).
- The relatively poor response rate for cetuximab alone (10-13%) masks that many more patients (40%) experience SD and oftentimes experience minor tumor shrinkage. By improving inhibition of an EGFR parallel pathway and achieving synergistic tumor inhibition we expect a substantial proportion of SD assessments to convert to responses.
- The response rates for cytotoxic chemotherapies are generally in this range and it is appropriate that an effective targeted therapy (with most head and neck SCCs expressing both relevant targets) would be similarly effective.
- As a secondary outcome measure we will evaluate continuous tumor shrinkage, which will increase power and allow us to detect a smaller difference.
- Furthermore as a secondary outcome we will evaluate PFS. We are not adequately powered to use PFS as a primary outcome given the sample size limitation. Nevertheless a PFS trend/signal comparable to NSCLC data would provide support to consider further evaluation in a follow-up study and the design would be straightforward given the data from this study to pick the optimal treatment and clinical setting.

Early evaluation for toxicity: For safety evaluation we have scheduled an interim safety evaluation after treatment of 3 and 6 patients with the combination of ARQ 197 (tivantinib) /cetuximab. If less than 2 of 6 patients experience severe toxicities / “DLTs”, the trial will continue, although we will continue to monitor adverse events per standard AE evaluation and reporting guidelines.

Early evaluation for futility:

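### Section 13.4 defines tumour burden by a sum that section 11 does not collect for nodes, and compares it without the baseline sum or HPV status

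*Combined protocol and SAP*

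**What the plan says.** Section 13.2 introduces continuous tumour shrinkage as a secondary outcome "which will increase power and allow us to detect a smaller difference".

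Section 13.4 defines it as the change from baseline to 8 weeks in the "sum of longest diameters of target lesions". The planned comparison is: "Early change in tumor burden will be compared between groups using two-sample t-tests". If deaths before week 8 or dropouts occur, "nonparametric Wilcoxon rank-sum tests will be performed in place of t-tests", and those patients receive the worst rank. Section 13.4 does not say whether change is absolute or relative, and it names no covariate, stratum, significance level or sidedness for this comparison.

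Section 11.1.2 defines the sum of target-lesion diameters differently: "longest for non-nodal lesions, short axis for nodal lesions". It also says that malignant nodes are measured and followed on the short axis alone.

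Randomisation uses permuted blocks stratified by HPV status (section 13.6). Section 13.3 says that no efficacy analysis will be based on that stratification, whose main purpose is comparability of the arms.

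**The concern.** There are two separate problems.

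The first is the definition. Section 3.1.2 accepts a node of at least 15 mm on the short axis as measurable disease, so nodal target lesions are to be expected in this population. For those patients section 13.4 asks for a diameter that section 11 does not collect. With the scale of change also unstated, two analysts could build different endpoint datasets from the same scans.

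The second is precision. The endpoint is included because it can detect a smaller effect than response rate can. Yet its comparison leaves out two baseline variables already in hand: the baseline sum, which section 11.1.2 requires, and HPV status, which must be known before randomisation. The test named first is also unlikely to be the one used, so the plan in practice rests on an unadjusted rank test.

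**Working it through.** **1. The plan's own sample size.** Inputs from section 13.2: 12% vs 35%, one-sided 0.10, 80% power, "using a continuity-corrected chisquare test".

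- Uncorrected n = [1.2816·√(2·0.235·0.765) + 0.8416·√(0.12·0.88 + 0.35·0.65)]² / 0.23² = (0.768 + 0.486)² / 0.0529 = 29.7.
- Corrected n = (29.7/4)·[1 + √(1 + 4/(29.7·0.23))]² = 37.9, so 38 per arm.

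The stated figure reproduces.

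**2. Does the continuous endpoint raise power at all?** Assume that response is a cut of a normally distributed shrinkage variable, and carry over the primary test's one-sided 0.10.

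- Implied standardised difference: z(0.35) - z(0.12) = -0.385 + 1.175 = 0.79.
- Power of an unadjusted t-test with 38 per arm: Φ(0.79/√(2/38) - 1.2816) = about 98%.
- Difference detectable at 80% power: (1.2816 + 0.8416)·√(2/38) = 0.487, which corresponds to about 12% vs 25% response.

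So section 13.2's claim is plausible even for the unadjusted test.

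**3. The two sums side by side.**

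| Target lesion | Section 13.4 needs | Section 11.1.2 collects |
|---|---|---|
| Non-nodal | longest diameter | longest diameter |
| Nodal | longest diameter | short axis only |

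The second row cannot be filled from the planned measurements.

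**4. How likely is the switch to Wilcoxon?** The chance of at least one early death or dropout among 76 is 1 - (1 - q)^76. The documents give no q, so a range is assumed.

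| q per patient | Chance of at least one |
|---|---|
| 1% | 53% |
| 2% | 78% |
| 5% | 98% |

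**5. Does the switch harm type I error?** In simulation (38 per arm, one-sided 0.10, 6,000 runs per setting, equal loss of 0 to 15% in both arms) the switching rule rejected under the null in 0.098 to 0.101 of runs. It did not inflate the error.

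**6. What does adjustment add?** The documents give no SD, correlation or dropout rate. Assumptions: 38 per arm, median baseline sum 60 mm (log SD 0.6), log-ratio SD 0.30, treatment effect -0.15, HPV effect -0.2, 40% HPV-positive, 12% early failures given the worst rank, one-sided 0.10, 3,000 runs per setting (simulation error about 1 point). Power by the correlation between baseline size and log ratio:

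| Correlation | Wilcoxon, mm change | Wilcoxon, log ratio | Adjusted rank test, log ratio |
|---|---|---|---|
| 0 | 0.555 | 0.613 | 0.618 |
| 0.3 | 0.590 | 0.605 | 0.632 |
| 0.5 | 0.625 | 0.613 | 0.666 |

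- Adjustment with the scale held fixed (fourth column minus third): +0.5, +2.7 and +5.3 points. With no HPV effect the gains are about -1, +1 and +4.
- Change of scale alone (third column minus second): +5.8, +1.5 and -1.2 points. Repeat runs put this between about -2 and +11.

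**The case against.** The strongest defence is that nothing here is invalid. The unadjusted test holds its level. Leaving HPV out of the efficacy analysis is a choice that section 13.3 states openly. The endpoint is secondary. The parenthetical in section 13.4 can be read as loose shorthand for the sum that section 11.1.2 says will be calculated, so usable data will exist. All of this stands. It limits the point to a definition that needs correcting and a modest loss of efficiency.

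Three stronger readings are tempting, and the documents do not support them.

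- A reader might infer that the test is picked after seeing the results. The switch is a fixed rule triggered by early death or dropout, not by the treatment effect or a normality check, and step 5 shows no inflation.
- A reader might compare Wilcoxon on millimetres with an adjusted rank test on the log ratio and credit the whole difference to adjustment. That comparison changes two things at once, and section 13.4 never says that change is in millimetres.
- A reader might infer that section 13.2's power rationale fails. It concerns shrinkage against dichotomised response, and step 2 supports it.

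**Conclusion.** The point holds in a limited form. The conflict between section 13.4 and section 11.1.2 is certain and needs no assumption. The omission of the baseline sum and HPV status costs efficiency, not validity. Its size cannot be fixed from the documents: under the assumptions in step 6 it is roughly 0 to 5 points of power, near zero unless baseline size is materially correlated with proportional shrinkage. Nothing in the documents establishes such a correlation, or an HPV effect on shrinkage. Stating the scale may matter as much as adjusting, but only if millimetres were intended. The worst-rank Wilcoxon test is probably the real analysis, so it should be named as such. The primary response-rate test and its sample size do not change.

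**What to change.** In section 13.4:

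- Replace the sum with the one in section 11.1.2 (longest diameter for non-nodal lesions, short axis for nodes).
- Define change as the ratio of the week-8 sum to the baseline sum.
- Name one main test whether or not losses occur: early deaths and dropouts given the worst rank, compared by rank ANCOVA with HPV status and baseline sum as covariates. A van Elteren test stratified by HPV is a simpler alternative, but stratifying by HPV alone leaves the baseline sum unused.
- Remove the conditional t-test. Label any ANCOVA among patients scanned at week 8 as supportive only, because it conditions on survival and continuation in an open-label trial.

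In section 13.3, amend the sentence on the HPV stratification so that it allows this adjustment.

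The cost is wording in two sections, with no new data. The downside is that an adjusted rank result is less familiar and gives no readily interpretable effect estimate; the planned waterfall plots can help readers see the size of the effect.

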04/15/14	Amendment #5. Provided clarification of how ARQ 197 should be taken under subsection 3.1.9. Updated Adverse Event Expedited Reporting System (AdEERS) with CTEP Adverse Event Reporting System (CTEP-AERS) throughout the protocol. Provided clarification about administration via G-tube under section 8.1. Provided clarification in the study calendar under section 10.0.
02/01/16	Amendment #6. Changed the local PI at Indiana University from [name] to [name].
04/19/16	Amendment #7. Updated CAPER for ARQ197 (tivantinib) version 2.2, February 19, 2016

SCHEMA

Primary Outcome:
Response Rate (RECIST)**

Secondary Outcomes:

- a) Continuous tumor shrinkage**
- b) PFS**
- c) OS**
- d) Outcomes a)-c) will be analyzed in tumors with c-MET copy number >5 and/or high expression (IHC)**

Please note: Patients who fail cetuximab as a single agent have the option to receive ARQ 197 (tivantinib) single agent afterwards..

CT scan assessment of response / tumor measurements (RECIST) will be every 2 cycles (=8 weeks) for all patients.

TABLE OF CONTENTS

	Page
SCHEMA	5
1. OBJECTIVES	8
1.1 Primary Objectives	8
1.2 Secondary Objectives	8
2. BACKGROUND	8
2.1 Study Disease	8
2.2 CTEP IND agent	9
2.3 Cetuximab (commercial)	17
2.4 Rationale	18
2.5 Correlative Studies Background	20
3. PATIENT SELECTION	21
3.1 Eligibility Criteria	21
3.2 Exclusion Criteria	22
3.3 Inclusion of Women and Minorities	24
4. REGISTRATION PROCEDURES	24
4.1 General Guidelines	24
4.2 Registration Process	25
5. TREATMENT PLAN	25
5.1 Agent Administration	26
5.2 General Concomitant Medication and Supportive Care Guidelines	27
5.3 Duration of Therapy	29
5.4 Duration of Follow Up	30
5.5 Criteria for Removal from Study	30
6. DOSING DELAYS/DOSE MODIFICATIONS	31
7. ADVERSE EVENTS: LIST AND REPORTING REQUIREMENTS	37
7.1 Comprehensive Adverse Events and Potential Risks Lists (CAEPRs)	37
7.2 Adverse event list(s) for commercial agent	39
7.3 Adverse Event Characteristics	39
7.4 Expedited Adverse Event Reporting	40
7.5 Routine Adverse Event Reporting	42
7.6 Secondary Malignancy	42
7.7 Second Malignancy	42
8. PHARMACEUTICAL INFORMATION	42
8.1 CTEP IND agent	42
8.2 Cetuximab (commercial)	44

9. BIOMARKER, CORRELATIVE, AND SPECIAL STUDIES	46

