1.2. Secondary Objectives

a) Continuous tumor shrinkage

b) PFS

c) OS

d) Endpoints a), b), and c) above, as well as response rates, will be assessed and compared between treatment arms in the subgroup of patients with high c-MET expression (anticipated to be ~84% of patients (*Seiwert et al, Cancer Research, 2009*), and/or high c-MET copy number (anticipated >10% and largely overlapping with MET IHC (*Seiwert et al, Cancer Research, 2009*)).

e) Single agent activity for ARQ 197 (tivantinib) in patients who have failed cetuximab

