c-Met can be activated in both a ligand-dependent manner, by the overexpression of c-Met and/or its ligand HGF, or a ligand-independent manner as in the case of activating mutations of c-Met such as those described in sporadic and hereditary papillary renal carcinoma (*Birchmeier et al., 2003*). Activation and autophosphorylation of c-Met results in the binding and phosphorylation of adaptor proteins such as Gab1, Grb2, Shc and c-Cbl, and results in the subsequent activation of signaling pathways, including the PI3K/Akt, FAK, STAT and Ras/MEK/Erk pathways that play various roles in cell survival, proliferation, invasion, and angiogenesis (*Furge et al., 2000; Christensen et al., 2003*). In the melanocyte lineage, c-Met expression is upregulated by microphthalmia-associated transcription factor (MITF), which has been implicated in the oncogenesis of melanoma and other cancers (*Levy et al., 2006; McGill et al., 2006*).

The presence of c-Met in most cancers, and its role in controlling multiple signal transduction pathways involved in tumor growth render this enzyme a logical therapeutic target for human cancer.

ARQ 197 (tivantinib) is a potent RTK inhibitor with high selectivity for the c-Met RTK, as determined by biochemical and cellular assays. A comprehensive review of ARQ 197 (tivantinib) can be found in the ARQ 197 (tivantinib) Investigator's Brochure (2010).

Tivantinib also appears to have anti-tubulin activity, and may act as a cytotoxic. Some investigators believe that the anti-tubulin activity contributes more to tivantinib's anti-cancer activity than the anti- c-Met activity (Michieli et al., 2013)

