2.4 Rationale

EGFR is expressed at very high levels in >90% of Head and Neck cancers (HNC; >NSCLC) and treatment with cetuximab (alone or in combination with chemotherapy or radiation) is now considered a standard of care. Nevertheless the response rate to EGFR inhibitors (cetuximab response rate = 13%, 40-50% stable disease) and median progression free survival of 70 days (*Vermorken et al, JCO, 2007*) remain disappointing. While treatment benefit is generally considered to be comparable to cytotoxic therapies with lower toxicity, the potential of EGFR as a therapeutic target in this highly EGFR expressing disease has not been fully exploited. Clinically treatment for recurrent/metastatic disease is either given in combination with chemotherapy (EXTREME) or after initial cytotoxic chemotherapy.

In our translational and preclinical work we demonstrated the following:

Eighty-four percent of the HNC samples showed c-MET overexpression (>NSCLC), and 18 of 20 HNC cell lines (90%) expressed c-MET. HGF overexpression was present in 45% of HNC. c-MET inhibition with SU11274/PF-2341066 abrogated c-MET signaling, cell viability, motility/migration in vitro, and tumor angiogenesis in vivo. Increased c-MET gene copy number was present with >10 copies in 3 of 23 (13%) tumor tissues. A greater-than-additive inhibition of cell growth was observed when combining a c-MET inhibitor with an EGFR inhibitor and synergy was mediated via erbB3 signaling. Finally we identified single nucleotide variants/mutations in the semaphorin (T230M/E168D/N375S), juxtamembrane (T1010I/R988C), and tyrosine kinase (T1275I/V1333I) domains (incidence: 13.5%) although functional contribution of these variants will require further study.

We demonstrated that c-MET is functionally important in HNC with prominent overexpression, and increased gene copy number, in the vast majority of HNC. c-MET inhibition abrogated c-MET functions, including proliferation, migration/motility, and angiogenesis. We concluded that c-MET is a promising, novel target for HNC and combination approaches with EGFR inhibitors should be explored.

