The importance of c-MET in general for head and neck cancers and a relationship to EGFR signaling is well supported by corroborative literature: Knowles et al demonstrated the importance of HGF and c-MET for HNC independently (Knowles, et al Clinical Cancer Research 2009). Particular emphasis was put on the tumor fibroblast HGF production. Furthermore recent data from the Univ. of Pittsburgh (California Consortium) show strong synergy of c-MET with EGFR inhibition, and extensive crosstalk between the two receptors (Xu et al, Clinical Cancer Research, 2011).

Both EGFR and c-MET signal downstream via the common signaling adaptor/receptor erbB3, as demonstrated for NSCLC previously and confirmed for HNC (Seiwert et al, Cancer Research 2009). Preclinical co-targeting of EGFR and MET revealed strong synergy in HNC (Seiwert et al, 2009, Cancer Research; Xu et al, 2011, Clinical Cancer Research). Furthermore two phase II randomized studies in NSCLC have yielded positive results suggesting that c-MET inhibition can augment the efficacy of EGFR inhibition and improve PFS in biomarker defined patient populations. EGFR and MET signaling are overlapping and it is well established that one can compensate for the other and joint inhibition provides benefit/synergy. It is crucial to identify the correct biologic subgroup/s that benefit most. Our preclinical work as well as NSCLC lung cancer data suggest that increased c-MET copy number and c-MET expression are the most likely candidate predictive biomarkers also for HNC.

Based on these preclinical findings we now propose to study the EGFR inhibitor cetuximab and the c-MET inhibitor ARQ 197 (tivantinib) in combination.

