3. PATIENT SELECTION

3.1 Eligibility Criteria

Inclusion Criteria:

- 3.1.1 Histologically / cytologically confirmed diagnosis of squamous cell carcinoma of Head and Neck origin not amenable to curative intent therapy. Both HPV(+) and HPV(-) are eligible, but status has to be known prior to randomization (although not required for consenting). Any type of tissue based HPV assessment is acceptable (e.g. p16 IHC or HPV ISH). If local HPV testing is not available slides can be sent to the University of Chicago for HPV testing. Please note that p16 IHC is generally only considered to be accurate for oropharyngeal tumors.
- 3.1.2 Presence of measurable lesions (as per RECIST 1.1). Generally a ≥ 10 mm tumor lesion (in the longest diameter by CT scan) or a Lymph node ≥ 15 mm (short axis) is considered measurable disease when evaluated by CT scan (with a slice thickness no greater than 5 mm). Please review full RECIST 1.1 criteria ([Eisenhauer EA et al, Eur J Ca, 2009](#)) as well as Section 11 for further details.
- 3.1.3 Availability of tissue (10 tumor containing FFPE slides/sections)
- 3.1.4 ECOG performance status of 0, 1 (see Appendix A).
- 3.1.5 Patients who have received cetuximab or another inhibitor of EGFR in the curative intent treatment setting (e.g. with radiation or during induction chemotherapy (prior to definitive, curative intent therapy)) are eligible for the study.
- 3.1.6 Age ≥ 18 years.

Because no dosing or adverse event data are currently available on the use of ARQ 197 (tivantinib) in patients < 18 years of age, children are excluded from this study, but will be eligible for future pediatric trials.

- 3.1.7 Life expectancy of greater than 8 weeks.
- 3.1.8 Patients must have normal organ and marrow function as defined below:

- hemoglobin	≥ 9.0 g/dL
- leukocytes	$\geq 3,000$ /mcL
- absolute neutrophil count	$\geq 1,500$ /mcL
- platelets	$\geq 100,000$ /mcL
- total bilirubin	≤ 1.5 X institutional upper limit of normal
- AST(SGOT)/ALT(SGPT)	≤ 2.5 X institutional upper limit of normal
- serum creatinine	≤ 1.5 X institutional upper limit of normal

OR

– creatinine clearance ≥ 60 mL/min/1.73 m² for patients with creatinine levels above institutional normal.

- 3.1.9 Patients must be able to swallow ARQ 197 (tivantinib) by mouth, unless adequate data about administration by G-tube becomes available. Tablets may be crushed, but must be taken orally.

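### The c-MET arm comparison is specified only in c-MET-high patients, with no marker-low estimate or treatment-by-marker term, although the plan treats c-MET as a candidate predictive marker

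*Combined protocol and SAP*

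**What the plan says.** **The arm comparison by marker.** Section 13.4 plans that every primary and secondary endpoint be "compared between treatment arms among the subgroup of patients with high c-MET expression and/or high c-MET copy number in an exploratory fashion". Secondary objective 1.2(d) uses the same restriction: the endpoints "will be assessed and compared between treatment arms in the subgroup of patients with high c-MET expression", or with high copy number. Section 13.1(d) repeats it. The schema gives a copy-number threshold: its outcomes "will be analyzed in tumors with c-MET copy number >5 and/or high expression (IHC" positive tumours. No IHC cut-off is stated for this trial.

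**The regression models.** Section 13.4 also plans logistic and Cox models for the effects of laboratory correlates on response, PFS and OS. They are not restricted to c-MET-high patients, but their terms are not listed.

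**The purpose.** Section 2.4 states: "It is crucial to identify the correct biologic subgroup/s that benefit most". It says that copy number and expression "are the most likely candidate predictive biomarkers also for HNC". Section 9.1 gives the value of finding a predictive marker as the hypothesis and says that the markers will be retrospectively validated.

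**The competing explanation.** Section 2.2.1 records: "Tivantinib also appears to have anti-tubulin activity, and may act as a cytotoxic". It adds that some investigators think this contributes more to the drug's activity than c-MET inhibition does.

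**The data.** Section 3.1.3 requires "Availability of tissue (10 tumor containing FFPE slides/sections" per patient. Section 9.2 lets the principal investigator grant exceptions. Marker-low patients should therefore be identifiable.

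**The concern.** A marker is predictive if the treatment effect differs between marker-high and marker-low patients. That is a contrast of two arm effects, and the plan names only one of them. A benefit in c-MET-high patients is what one would see if c-MET selects the patients who benefit. It is equally what one would see if the combination works regardless of c-MET, and Section 2.2.1 makes that alternative a live one.

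For IHC, the named subgroup is also expected to be about 84% of the trial, so its result will largely repeat the overall result. At stake is the biomarker conclusion carried into a follow-up study: a positive high-only result could be read as support for selecting on c-MET when it carries no such information.

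**Working it through.** **Inputs from the documents.** 76 evaluable patients, 38 per arm; 12% vs 35%; one-sided 0.10; continuity-corrected chi-square (13.2). IHC-high about 84%; copy-number-high above 10% and largely overlapping with IHC (1.2(d)). For copy number, Section 2.4 reports: "Increased c-MET gene copy number was present with >10 copies in 3 of 23 (13%) tumor tissues".

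**Assumptions, not in the documents.** Marker-high response is 12% vs 35%. In marker-low patients it is either 12% vs 35% (*not predictive*) or 12% vs 12% (*fully predictive*). The primary test level is reused, since none is given for subgroups. Marker groups split evenly by arm.

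**Step 1: the plan's own figure.** With mean rate 0.235 and difference 0.23:

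- Uncorrected n' = [1.2816·√(2·0.235·0.765) + 0.8416·√(0.12·0.88 + 0.35·0.65)]² / 0.23² = 29.7.
- Corrected n = (n'/4)·[1 + √(1 + 4/(n'·0.23))]² = 37.9, so 38 per arm. This reproduces the plan. Exact power at 38 per arm is 81.6%.

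**Step 2: group sizes.** IHC: 76 × 0.84 = 63.8, about 32 high and 6 low per arm. Copy number alone at 13%: 76 × 0.13 = 9.9, about 5 high and 33 low per arm. If the and/or definition is read as a union, with copy number largely overlapping IHC, the IHC split applies.

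**Step 3: what the planned comparisons show.** Exact binomial enumeration of the continuity-corrected test:

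| Probability of significance | Not predictive | Fully predictive |
|---|---|---|
| IHC (32/6): high-only | 74.2% | 74.2% |
| IHC (32/6): all patients | 81.6% | 71.2% |
| IHC (32/6): both | 72.2% | 68.3% |
| Copy number (5/33): high-only | 12.7% | 12.7% |
| Copy number (5/33): all patients | 81.6% | 10.9% |

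The high-only rate is identical in both columns because marker-low outcomes do not enter it. For IHC, reading it beside the all-patient test adds little. For copy number alone, the all-patient test does separate the scenarios. The 13% is itself uncertain: the exact 95% CI for 3 of 23 is 3% to 34%, and it refers to more than 10 copies, whereas the schema uses more than 5. At 34% high (13/25 per arm) the all-patient rates are 82% vs 26%.

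**Step 4: what the missing analysis would give.** The 95% half-width for the IHC-low arm effect, 6 per arm:

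- 12% vs 35%: 1.96·√[(0.1056 + 0.2275)/6] = 0.46.
- 12% vs 12%: 1.96·√[2·0.1056/6] = 0.37.

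For the interaction I used the difference in log odds ratios with 0.5 added to each cell, which is the Firth estimate for this saturated model, tested one-sided at 0.10. The rate depends on the standard error: the lower figure in each range uses the Fisher information at the penalised estimate, the higher one the augmented counts.

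| Interaction positive | Not predictive | Fully predictive |
|---|---|---|
| IHC (32/6) | 8.9–10.6% | 23.1–26.8% |
| Copy number (5/33) | 1.2–2.0% | 16.5–19.3% |

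An ordinary logistic interaction for IHC would meet an empty or full cell, and so have no finite estimate, in 51% (not predictive) or 72% (fully predictive) of trials.

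**The case against.** **The analysis matches the listed objectives.** Objective 1.2(d), Section 13.1(d) and the schema ask for a comparison in c-MET-high patients; 13.4 delivers it and labels it exploratory. No listed endpoint is a test of prediction. This stands, and it limits the weight of the point. It does not remove the mismatch with 9.1, which sets out to validate the markers.

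**The regression models could already do this.** They cover all patients and could carry an interaction. As worded, though, they describe marker effects on outcome, which are prognostic. Naming the terms is most of the fix.

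**For response, the marker-low data are implicit.** All-patient counts minus marker-high counts give marker-low counts by arm, provided marker status is complete. This is correct, so the significance rates above understate what a careful reader could extract. But the subtraction is not planned, and it does not work directly for PFS or OS.

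**The added analysis is weak.** This also stands. The interaction rates are low even in the all-or-none scenario, and a partial interaction would be harder to see. The case for the change is honest estimation, not power.

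**Stronger readings to avoid.** A reader might infer that the trial cannot speak to c-MET prediction at all; the two points on implicit counts and unrestricted models, and the copy-number results, contradict that. A reader might also infer that data collection is deficient or that the primary conclusion is at risk; the tissue requirement and the exploratory label do not support either.

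**Conclusion.** The point holds in limited form. The documents name a c-MET-based arm comparison only in marker-high patients and specify neither a marker-low estimate nor a treatment-by-marker term, while 2.4 and 9.1 look for a predictive marker. Taken alone, the named comparison is uninformative on that question. The indistinguishability of the planned comparisons applies to IHC at about 84% high and to the and/or union; it does not apply to copy number read alone.

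The figures rest on the assumed marker-low response rates, the reused one-sided 0.10 level, even splits by arm and complete marker data. The identity of the high-only result across the two scenarios does not depend on these values; it follows from leaving marker-low patients out.

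This is a minor-to-moderate, inexpensive improvement to a secondary exploratory analysis.

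**What to change.** In 13.4:

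1. State that the planned logistic and Cox models include treatment, marker and treatment-by-marker terms, fitted separately for IHC and copy number.
2. Report the arm effect with a 95% CI in both marker-high and marker-low patients for response, tumour shrinkage, PFS and OS. Shrinkage lies outside those models, so give its arm difference within each marker group.
3. Fix the IHC cut-off before marker results are linked to outcome, and use the schema's threshold of more than 5 for copy number. Continuous copy number is optional.
4. Use a penalised (Firth) or exact method where cells are sparse, and name the standard error or interval method.
5. Base any statement about prediction on the interaction estimate, and label it exploratory.

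In 9.1, change the stated intention from validating the markers to exploring them.

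The cost is a few lines of text and minor programming, with no new samples or visits. The downside is a more modest biomarker conclusion: the IHC-low effect will carry an interval of roughly ±37 to 46 points, and the interaction will usually be inconclusive.
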